8.2 Premature Study Discontinuation

- Subject repeatedly noncompliant with study treatment as prescribed.
- Request by the subject to withdraw or not able to attend study visits as required by study.
- Request of the primary care provider if s/he thinks the study is no longer in the best interest of the subject.
- Subject judged by the investigator to be at significant risk of failing to comply with the provisions of the protocol as to cause harm to self or seriously interfere with the validity of the study results.
- At the discretion of the institutional review board (IRB), Office for Human Research Protections (OHRP), NIAID, investigator, or IDSMB.

9.0 STATISTICAL CONSIDERATIONS

9.1 General Design Issues

This study is a randomized, placebo-controlled, two-arm, single-site, pilot study that will

evaluate whether 12 weeks of treatment with DP, decreases markers of immune activation and systemic inflammation in HIV-1 infected subjects virally suppressed on ART. DP will be administered to subjects for up to 24 weeks. Follow-up continues to week 28. The targeted sample size will be 40 subjects (20 of these subjects will be enrolled in the rectal tissue subset).

9.2 Endpoints

9.2.1 Primary Endpoints

- Change in Plasma level of sCD14 from baseline to week 12.
- Change in Plasma level of sCD163 and IL-6 from baseline to week 12.

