DESIGN This is a Phase 1/2, randomized, double blind, two-arm, partial cross-over, single-site, pilot study evaluating the effect of oral dipyridamole (DP) on immune activation and inflammation in HIV-1-infected, ART-treated subjects with HIV-1 RNA less than 50 copies/mL. The change from baseline to week 12 in the plasma levels of sCD163 and sCD14, and IL-6 will be assessed within and compared between study arms, as will secondary endpoints related to immune activation, inflammation, gut mucosal changes, pulmonary function and brachial artery flow-mediated dilation (FMD).

Subjects will be randomized 1:1 to DP 100 mg 4 times a day or matching placebo. Following week 12, subjects in the DP arm will continue DP for an additional 12 weeks (for total 24 weeks) and subjects in the placebo arm will cross over to DP 100 mg 4 times a day for 12 weeks.

Evaluations will be scheduled at Entry (week 0) and Weeks 2, 4, 8, 12, 14, 16, 20, 24, and 28.

DURATION Subjects will be in the study for 28 weeks.

[figure not shown]
SAMPLE SIZE 40 subjects, 20 per arm. Rectal Tissue Subset: 20 subjects, 10 per arm.

POPULATION HIV-1-infected male and female subjects, 18 years of age or older, on ART with HIV-1 RNA <50 copies/mL for a minimum of 12 months.

STRATIFICATION Subjects will be stratified by CD4+ T-cell counts (≤ 500 versus > 500 cells/mm³, and by enrollment into the Rectal Tissue Subset)

REGIMEN
Arm A: Dipyridamole 100 mg 4 times daily for 24 weeks
Arm B: Dipyridamole placebo 1 capsule 4 times daily for 12 weeks, then Dipyridamole 100 mg 4 times daily for 12 weeks.

STUDY SCHEMA:

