6.0 CLINICAL AND LABORATORY EVALUATIONS

6.1 Schedule of Events (SOE)

| Evaluation | Screening | Pre-Entry ¹ | Entry | Week | | | | | | | | Premature Treatment and/or Study Discontinuation | | |
|--|-----------|------------------------|-------|------|---|---|----|----|----|----|----|--|----|----------------|
| | | | | 2 | 4 | 8 | 12 | 14 | 16 | 20 | 24 | | 28 | |
| Documentation of HIV-1 infection | X | | | | | | | | | | | | | |
| Medical History/Medication History | X | | | | | | | | | | | | | |
| Complete Physical Exam | X | | | | | | | | | | | | | |
| Targeted Physical Exam | | X | X | | X | X | X | | X | X | X | X | | X |
| Clinical Assessments | | | X | | X | X | X | | X | X | X | X | | X |
| Concomitant Medications | | X | X | | X | X | X | | X | X | X | X | | X |
| Hematology | X | | X | | | | X | | | | X | | | X |
| Liver Function Tests/Blood Chemistries | X | | X | | X | | X | | X | | X | | | X |
| Fasting Lipid Panel | | | X | | | | X | | | | X | | | X |
| Plasma HIV-1-1 RNA | X | | X | | | | X | | | | X | | | X |
| CD4+/CD8+ | X | | X | | | | X | | | | X | | | X |
| Pregnancy Test | X | | X | | X | X | X | | X | X | X | X | | X |
| Prothrombin time/INR/PTT ² | | X | | | | | | | | | | | | |
| Hepatitis B and C | X | | | | | | | | | | | | | |
| Stored Plasma for Immunology/Virology ⁵ | | X | X | | X | | X | | X | | X | X | | X |
| Stored PBMC for Immunology/Virology ⁵ | | X | X | | X | | X | | X | | X | X | | X |
| Urine adenosine level (stored) ⁵ | | | X | | X | | X | | X | | X | | | X |
| Serum for Dipyridamole concentration (stored) | | | | | X | X | X | | X | X | X | | | X |
| Brachial Artery FMD | | | X | | X | | X | | | | X | | | X ³ |
| Rectal swabs for GC/CT NAAT ² | X | | X | | | | X | | | | X | X | | |
| HSV Serology ² | | | X | | | | | | | | | | | |
| Flexible sigmoidoscopy (rectal biopsy) ^{2, 5} | | | X | | | | X | | | | X | X | | |
| Adherence self-report | | | | | X | | X | | X | | X | | | |

| Evaluation | Screening | Pre-Entry ¹ | Entry | Week | | | | | | | | Premature Treatment and/or Study Discontinuation | |
|--|-----------|------------------------|-------|------|---|---|----|----|----|----|----|--|----|
| | | | | 2 | 4 | 8 | 12 | 14 | 16 | 20 | 24 | | 28 |
| Medication Adherence Assessment ⁴ | | | X | | X | | X | | X | | X | | |
| Telephone assessment of tolerability/adherence | | | | X | | | | X | | | | | |
| Pre- and post-bronchodilator spirometry ⁶ | | | X | | X | | X | | | | X | | |

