9.2.2 Secondary Endpoints

- Changes from entry to week 12 and 24 (as applicable) in the following:
 - %HLA-DR+ CD38+ expression in CD8+ and CD4+ T-cells
 - %CD69+CD25+ expression in CD4+ and CD8+ T-cells
 - CD16 and tissue factor expression in monocytes
 - Plasma levels of biomarkers of systemic inflammation (sTNF α R, TNF α , hsCRP) and coagulation (D-dimer, tissue factor)
 - Percent brachial artery FMD
 - Proportion of cycling CD4+ and CD8+ T cells as measured by Ki-67 expression
- Grade 2 or higher AEs, treatment discontinuations
- Correlation of plasma DP level to urine adenosine, plasma IL-6, and soluble and cellular markers of immune activation

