9.5 Primary Analyses

As this is a pilot study of biologic activity, our primary analysis of efficacy will be an as-treated analysis, limited to subjects who have data for baseline and week 12, and remain on study treatment through week 12 with no more than 7 consecutive days of medication

missed, and did not change ART or use prohibited medications or have virologic failure during this time period. To preserve the study power in the case of greater than 10% missing data due to discontinuation/non-adherence, additional subjects may enroll, at discretion of the protocol team, to replace subjects who are discontinued or non-adherent to study product or scheduled study visits prior to week 12. Therefore the total sample size may exceed 40 at the end of the study.

Changes from baseline to week 12 in sCD14, sCD163, and IL-6 (as well as all secondary and exploratory outcomes) will be summarized by means, medians, standard deviations, and 95% confidence intervals for each treatment arm. We will compare the two study arms at baseline with respect to clinical characteristics as well as subject demographics. Any baseline covariates that cause imbalance at the 5% significance level will be included in the primary analyses. Our primary analysis will utilize an Analysis of Covariance (ANCOVA) model of the primary outcomes, which compares the outcomes at 12 weeks between arms (placebo/DP) after adjusting for baseline activation (or plasma level) and CD4 cell count. If any of the primary outcomes violate assumptions of normality, suitable transformations will be investigated. If no transformation can be used, between-arm comparisons on 12 week change in sCD14, sCD163, and IL-6 will be assessed by the Wilcoxon rank sum test.

Statistical significance for the primary analysis of sCD14 will be tested using a two-sided $\alpha = 0.05$. The other key outcomes of sCD163 and IL-6 will each be tested at 0.05 as well.

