9.6 Secondary Analyses

Changes from baseline to week 12 and week 24 in other secondary and exploratory endpoints including measurements of immune activation, systemic inflammation, and residual virus in blood and rectal tissue, change in pre- and post-bronchodilator FEV₁, and percent FMD (see 9.2.2 and 9.2.3) will be summarized by means, medians, standard deviations, and 95% CIs for each of the treatment arms. As in the primary analysis, between-arm comparisons will be made using either an ANCOVA model or the Wilcoxon rank sum test. For secondary outcomes with more frequent measurements (i.e. baseline, 4, 12 week), longitudinal models such as Generalized Estimating Equations (GEE) will be used to compare the trajectories across time between treatment arms. Included in the model will be predictor variables for week, treatment group, and their interaction.

The study design allows for an additional 12 weeks of follow up in which the placebo arm crosses over to DP 100 mg 4 times daily for 12 weeks. As an exploratory measure, the trajectories of T cell activation and IL-6 expression for these subjects will be analyzed using a generalized linear mixed model with covariates for week (defined as time since initiating placebo/DP), drug (placebo/DP), and their interaction. The effects of long-term and short-term DP on T cell activation will be quantified using an ANCOVA model, similar to the primary analysis.

Safety will be evaluated by summarizing the number and frequency of Grade ≥ 2 adverse events within each study arm. Comparisons between study arms will be done

using Fisher's exact test at each study visit.

Statistical significance for each of the secondary analyses will be tested using the nominal 5% type I error rate.

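### Does the plan need to define baseline, and should it average the Pre-Entry and Entry samples, given that plasma is stored at both visits?

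*Combined protocol and SAP*

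**What the plan says.** The primary endpoint in Section 9.2.1 is "Change in Plasma level of sCD14 from baseline to week 12", with the same wording for sCD163 and IL-6. The ANCOVA in Section 9.5 compares Week 12 values between arms "after adjusting for baseline activation (or plasma level) and CD4 cell count". Its analysis set is restricted to participants with both baseline and Week 12 data. Neither section says which pre-treatment sample supplies baseline.

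Elsewhere the text points to Entry. The design summary has "Evaluations will be scheduled at Entry (week 0) and Weeks" and then the later visits, so Entry is time zero. The secondary and exploratory lists (Sections 9.2.2 and 9.2.3) open with "Changes from entry to week 12 and 24 (as applicable) in the following". Section 9.6 describes those same quantities as "Changes from baseline to week 12 and week 24 in other secondary and exploratory endpoints", so the two words are used interchangeably.

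In the Schedule of Events (Section 6.1), the row "Stored Plasma for Immunology/Virology" is marked at Pre-Entry and at Entry, as is the stored PBMC row. Pre-Entry falls within 14 days before Entry, Entry is normally at least 24 hours later, and both precede study drug (Sections 6.2.1 and 6.2.2). The rows "Fasting Lipid Panel" and "Brachial Artery FMD" are marked at Entry and Week 12 but not at Pre-Entry.

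**The concern.** Two things look wrong. First, a term that fixes the primary endpoint, the ANCOVA covariate and membership of the primary analysis set has no definition, although two pre-treatment samples could supply it. If the choice were left until results were visible, an analyst could pick among Entry, Pre-Entry and their mean.

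Second, the second sample appears to go unused. In a trial expecting 18 analysable participants per arm, averaging two pre-treatment values can reduce noise in the covariate and sharpen the comparison without a new visit or blood draw. The vaccination exclusion (Section 4.2.10) covers Pre-Entry and Entry alike, which would fit an intended two-sample baseline.

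**Working it through.** **The plan's own figures.** Inputs from Sections 9.4 and 9.5: two-sided 5% test, 80% power, SD 0.54 (all sCD14 values here are ×10⁶ pg/mL), 20 or 18 per arm. A two-sample t-test with the noncentral t distribution and 2n − 2 degrees of freedom gives detectable standardized differences of 0.9091 (20 per arm) and 0.9613 (18 per arm). Multiplied by 0.54 these are 0.491 and 0.519. They match the stated 0.909, 0.961, 0.49 and 0.52. They use no baseline adjustment, so the choice of baseline cannot make them wrong.

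**What averaging would do.** Let r₁ and r₂ be the correlations of the Pre-Entry and Entry values with Week 12, and ρ the correlation between the two pre-treatment values. The documents give none of these, so every value below is an assumption. Equal variances are also assumed. The residual variance, as a fraction of the Week 12 variance, is:

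- Entry alone: 1 − r₂²
- mean of the two: 1 − (r₁ + r₂)² / [2(1 + ρ)]

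The detectable difference scales with the square root of this. Power is for 18 per arm at the effect that Entry alone detects with 80% power.

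*Both samples equally predictive (r₁ = r₂ = r), with ρ > r because the samples are days apart:*

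| r | ρ | Entry | Mean | Change in detectable difference | Power |
|---|---|---|---|---|---|
| 0.5 | 0.6 | 0.750 | 0.688 | −4.3% | 83.3% |
| 0.5 | 0.9 | 0.750 | 0.737 | −0.9% | 80.7% |
| 0.7 | 0.8 | 0.510 | 0.456 | −5.5% | 84.2% |
| 0.7 | 0.9 | 0.510 | 0.484 | −2.6% | 82.0% |
| 0.8 | 0.9 | 0.360 | 0.326 | −4.8% | 83.7% |

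In absolute terms, at r = 0.7 and 18 per arm, Entry alone gives 0.961 × 0.54 × √0.510 = 0.371. The mean gives 0.350 (ρ = 0.8) or 0.361 (ρ = 0.9). At r = 0.3 with ρ from 0.5 to 0.9 the gain is only 0.3 to 1.7%. The limiting case ρ = r, for r from 0.5 to 0.8, gives 5.7 to 10.4%.

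*Pre-Entry less predictive than Entry:*

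| r₁ | r₂ | ρ | Entry | Mean | Change in detectable difference | Power |
|---|---|---|---|---|---|---|
| 0.65 | 0.7 | 0.9 | 0.510 | 0.520 | +1.0% | about 79% |
| 0.6 | 0.7 | 0.8 | 0.510 | 0.531 | +2.0% | about 78% |
| 0.5 | 0.7 | 0.6 | 0.510 | 0.550 | +3.8% | about 77% |

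Setting the two variances equal gives the break-even ratio r₁/r₂ = √[2(1 + ρ)] − 1, which is 0.79, 0.84, 0.90 and 0.95 for ρ = 0.6, 0.7, 0.8 and 0.9. The more closely the two samples agree, the smaller the shortfall in Pre-Entry that turns the gain into a loss.

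**Is such a shortfall plausible?** Sections 6.3.1 and 6.3.10 apply fasting and time-of-day rules to fasting evaluations and to FMD. Pre-Entry has neither, while Entry and Week 12 have both. The documents therefore do not require Pre-Entry plasma to be drawn under matched conditions. The laboratory processing chart cited in Section 6.3.9 may require it, but it is not part of these documents.

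**Cost.** One extra value per participant for three markers is 40 × 3 = 120 assays. The stored plasma and PBMC also serve virology (Sections 6.1 and 6.3.9), and no aliquot volumes are given.

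**The case for a change.** The strongest case for a change is that one sentence costs almost nothing, and the undefined term decides who enters the primary analysis: a participant with only a Pre-Entry value is in or out depending on the reading. The primary-endpoint assays are run in batch after follow-up ends (Section 9.7), so the definition could be fixed before any result exists. The gain could also be larger if the fallback Wilcoxon test on change scores is used. With equally predictive samples, r of 0.5 to 0.8, and ρ of 0.6 to 0.9 (ρ > r), averaging cuts change-score variance by 5 to 20%.

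Most of this is true, and a clarifying sentence would do no harm. But it would state what the text already implies. Under the Entry reading, a participant without an Entry value simply lacks baseline data, so the analysis-set rule can be applied as written. The batch timing also limits the opening for a data-driven choice. The Wilcoxon figures apply only if no transformation is adequate, and they assume, as the ANCOVA gains do, that Pre-Entry predicts Week 12 as well as Entry does.

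**Conclusion.** No change is called for. The missing definition is a gap that analysts would fill with the Entry (week 0) value. That reading follows from the visit numbering and from the interchangeable use of entry and baseline in Section 9. It gives a valid, unbiased comparison and leaves the stated power figures intact.

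Averaging is an optional refinement of uncertain sign. If both samples predict Week 12 equally well, with r from 0.5 to 0.8 and ρ from 0.6 to 0.9 (ρ > r), the detectable difference falls 0.9 to 5.5% and power rises from 80% to 81 to 84%. If Pre-Entry predicts somewhat less well, averaging costs 1 to 4% in the examples above, with power of 77 to 79%. All of these sizes rest on assumed correlations. Which case applies depends on collection conditions that the documents do not show. The plan gives up nothing established by using Entry alone.

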9.2.2 Secondary Endpoints

- Changes from entry to week 12 and 24 (as applicable) in the following:
 - %HLA-DR+ CD38+ expression in CD8+ and CD4+ T-cells
 - %CD69+CD25+ expression in CD4+ and CD8+ T-cells
 - CD16 and tissue factor expression in monocytes
 - Plasma levels of biomarkers of systemic inflammation (sTNF α R, TNF α , hsCRP) and coagulation (D-dimer, tissue factor)
 - Percent brachial artery FMD
 - Proportion of cycling CD4+ and CD8+ T cells as measured by Ki-67 expression
- Grade 2 or higher AEs, treatment discontinuations
- Correlation of plasma DP level to urine adenosine, plasma IL-6, and soluble and cellular markers of immune activation

9.2.3 Exploratory Endpoints

- Changes from entry to week 12 and 24 (as applicable) in the following:
 - Rectal tissue: %CD38+/DR+ CD4+ and CD8+ T-cells by flow cytometry
 - Blood and rectal tissue CCR9+ β 7^{high} T-cells
 - Frequency and numbers of CD73 expressing T cells B cells and monocytes in peripheral blood and gut

- Purine and adenosine levels in blood
- Plasma HIV-1 RNA using single copy assay (SCA)
- Cell-associated HIV-1 RNA and DNA in blood and rectal tissue
- Pre- and post-bronchodilator FEV₁

9.3 Randomization and Stratification

At study entry, subjects will be allocated at a 1:1 ratio to the two arms using blocked randomization. In addition, randomization will be stratified by CD4 cell count at screening (<500 cells/mm³ or ≥500 cells/mm³), and enrollment into the rectal tissue subset.

9.4 Sample Size and Accrual

There will be 40 subjects (20 per arm) randomized to either DP 100 mg 4 times daily or matching placebo, and it is assumed that no more than 10% of participants will be excluded from the primary analysis due to any reason. sCD14 will be the main primary outcome, while sCD163 and IL-6 will be treated as other key outcomes of interest. As a result, the hypothesis for sCD14 will be tested at the 5% significance level and will be the basis for our power analysis. sCD163 and IL-6 will also be tested at the 5% significance level each. Based on the assumption that none of the 40 subjects are excluded from the primary analysis for any reason, we will have 80% power to detect standardized mean difference of 0.909 between treatment arms for the sCD14. In terms of clinically meaningful effects, this translates to a difference of 0.49×10^6 pg/mL in sCD14 between arms at 12 weeks assuming similar standard deviation seen in preliminary data (standard deviation is 0.54×10^6 pg/mL for sCD14). In the more realistic situation that 10% of subjects are excluded (18 per arm), we will have 80% power to detect standardized mean difference of 0.961 between treatment arms for the primary outcome. In terms of clinically meaningful effects, this translates to a difference of 0.52×10^6 pg/mL in sCD14 between arms at 12 weeks assuming similar standard deviations seen in preliminary data.

Because the ANCOVA model will adjust for baseline sCD14 as well as CD4 cell count (neither of which are expected to be related to treatment arm), it's likely that there will be sufficient power to detect even smaller effects than what is expected.

It is anticipated that subjects will accrue to the study at a rate of 2-3 subjects per month. At this rate, the study should fully accrue within 18 months after the first subject enrolls.

9.5 Primary Analyses

As this is a pilot study of biologic activity, our primary analysis of efficacy will be an as-treated analysis, limited to subjects who have data for baseline and week 12, and remain on study treatment through week 12 with no more than 7 consecutive days of medication

missed, and did not change ART or use prohibited medications or have virologic failure during this time period. To preserve the study power in the case of greater than 10% missing data due to discontinuation/non-adherence, additional subjects may enroll, at discretion of the protocol team, to replace subjects who are discontinued or non-adherent to study product or scheduled study visits prior to week 12. Therefore the total sample size may exceed 40 at the end of the study.

Changes from baseline to week 12 in sCD14, sCD163, and IL-6 (as well as all secondary and exploratory outcomes) will be summarized by means, medians, standard deviations, and 95% confidence intervals for each treatment arm. We will compare the two study arms at baseline with respect to clinical characteristics as well as subject demographics. Any baseline covariates that cause imbalance at the 5% significance level will be included in the primary analyses. Our primary analysis will utilize an Analysis of Covariance (ANCOVA) model of the primary outcomes, which compares the outcomes at 12 weeks between arms (placebo/DP) after adjusting for baseline activation (or plasma level) and CD4 cell count. If any of the primary outcomes violate assumptions of normality, suitable transformations will be investigated. If no transformation can be used, between-arm comparisons on 12 week change in sCD14, sCD163, and IL-6 will be assessed by the Wilcoxon rank sum test.

Statistical significance for the primary analysis of sCD14 will be tested using a two-sided $\alpha = 0.05$. The other key outcomes of sCD163 and IL-6 will each be tested at 0.05 as well.

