- Abnormalities of the colorectal mucosa or significant colorectal symptom(s), which in the opinion of the study investigator represent a contraindication to biopsy (including but not limited to presence of any unresolved injury, infectious or inflammatory condition of the local mucosa, and presence of symptomatic external hemorrhoids.

NOTE: Abnormalities of the colorectal mucosa will be assessed at the time of the enrollment flexible sigmoidoscopy. If no significant colorectal abnormalities or symptoms are present then the participant will undergo the enrollment procedures. If abnormalities are present then no biopsies will be performed and the participant will not be enrolled into the rectal tissue subset but will continue participation in the main study.

- Active untreated gonorrhea, or chlamydia infection within 30 days prior to study entry (subjects diagnosed with rectal gonorrhea or chlamydia infection at screening may be treated during the screening period provided the treatment is at least 30 days prior to entry).

4.2.15 Exclusions for spirometry testing (for participants enrolled under Version 2.0): Participants will not undergo pre- and post-bronchodilator spirometry if they have any of the following:

- Abdominal or cataract surgery within 3 months.
- Myocardial infarction or stroke within the past 3 months.
- Acute onset of shortness of breath, cough, fever or heart condition such as tachycardia, angina or arrhythmias with 4 weeks prior to enrollment.
- Increasing respiratory symptoms or febrile (temperature >100.4°F [38°C]) within 4 weeks of study entry.
- Uncontrolled hypertension defined as systolic > 160 mm Hg or diastolic > 100 mm Hg from an average of two or more readings. Participant with controlled hypertension may undergo spirometry.
- Prior history of adverse reaction to albuterol

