6.3.6 Laboratory Evaluations

At screening and entry all protocol required laboratory values must be recorded on CRFs. For post-entry assessments, record on CRFs all Grade ≥ 2 laboratory values. All laboratory toxicities that led to a change in treatment, regardless of grade, must be recorded on CRFs. Record on CRFs all values for serum creatinine, AST, ALT, and fasting lipid panel regardless of grade.

Hematology

Hemoglobin, hematocrit, white blood cell count (WBC), differential WBC, and platelet count.

Liver Function Tests/Chemistries

Total bilirubin (and indirect bilirubin if subject is receiving atazanavir), ALT (SGPT), AST (SGOT), and alkaline phosphatase, blood urea nitrogen (BUN), creatinine, glucose, sodium, potassium, chloride, and CO₂/bicarbonate.

Fasting Lipid Panel

Total cholesterol, HDL-c, calculated LDL-c (if triglycerides <400 mg/dL) and triglycerides.

Hepatitis Testing (at Screening)

Hepatitis B surface antigen, Hepatitis C antibody (if indicated, Hepatitis C RNA PCR).

Prothrombin time/INR/PTT

Prothrombin time/INR and PTT are required at pre-entry for rectal tissue subset only.

Rectal GC/CT NAAT

Rectal swab for GC/CT NAAT will be obtained for rectal tissue subset only

HSV Antibody

Serum for HSV antibody testing will be obtained at Entry visit for the rectal tissue subset only

Pregnancy Test

For women of reproductive potential as defined in section 4.1.11, serum or urine β -HCG (urine test must have a sensitivity of at least 50 mIU/mL) must be performed as indicated in section 6.1:

- At the screening visit.
- At the study entry visit.
- Every 4 weeks during study participation.

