9.7 Monitoring

Accrual and a summary of all Grade ≥ 2 signs and symptoms, all Grade ≥ 2 laboratory abnormalities and all reported AEs will be reviewed by the study team monthly. This summary will be pooled over the study arms. In addition, baseline characteristics as well as early study treatment and study discontinuations, pooled over study arms, will be reviewed regularly by the team. The Center for Research in Health Care Data Center (CRHC DC) will also prepare a quarterly report of all Grade ≥ 2 signs and symptoms, all Grade ≥ 2 laboratory abnormalities and reported AEs by study arm, to be reviewed quarterly [or as requested] by the DAIDS clinical representative or designee.

Approximately 6 months after enrollment of the first subject, (or, if earlier, when 50% of subjects have been enrolled), an interim review of the study will occur. An Institutional Data Safety and Monitoring Board (IDSMB) convened by the University of Pittsburgh will function as a Study Monitoring Committee (SMC) for the study and will review accrual, toxicity summaries, and off-treatment and off-study rates and reasons broken down by study arms. In addition, longitudinal changes in CD4+ T-cell count and HIV-1 RNA levels will be reviewed. Note that immune activation measurements, including the primary endpoints, will be run in batch after follow-up is concluded. The first IDSMB review will occur when 30% of the subjects are enrolled or at 1 years, whichever is earlier. IDSMB reviews will occur at least annually after the first review or at more frequent intervals as determined by the IDSMB. An interim IDSMB review may also be conducted if a reason is identified by the DAIDS clinical representative, study investigators, or study statistician in consultation with the team.

The specific responsibilities of the IDSMB are to:

1. Review the research protocol, informed consent documents and plans for data and safety monitoring;
2. Evaluate the progress of the study, including periodic assessments of data quality and timeliness, subject recruitment, accrual and retention, subject risk versus benefit, adverse events, unanticipated problems, performance of the trial site, and other factors that can affect study outcome;
3. Consider factors external to the study when relevant information becomes available, such as scientific or therapeutic developments that may have an impact on the safety of the subjects or the ethics of the study;

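### The primary ANCOVA picks extra covariates by baseline imbalance at p<0.05 from an unlisted pool, and leaves out rectal-subset enrolment, one of the two stratification factors

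*Combined protocol and SAP*

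**What the plan says.** Section 9.5 describes a baseline comparison of the arms: "We will compare the two study arms at baseline with respect to clinical characteristics as well as subject demographics". It continues: "Any baseline covariates that cause imbalance at the 5% significance level will be included in the primary analyses". No variables, test or maximum number are given there or elsewhere in Section 9. The ANCOVA compares week 12 outcomes between arms "after adjusting for baseline activation (or plasma level) and CD4 cell count", and Section 9.4 names the same two adjustment terms.

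Section 9.3 stratifies randomisation by screening CD4 count "and enrollment into the rectal tissue subset". The synopsis agrees: "and by enrollment into the Rectal Tissue Subset". The subset is planned as 20 of the 40 subjects, 10 per arm. It does not appear in the primary model.

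Two other passages bear on the size of the problem. Section 6.3.6 says "At screening and entry all protocol required laboratory values must be recorded on CRFs", so the potential pool is large. Section 9.7 says that "immune activation measurements, including the primary endpoints, will be run in batch after follow-up is concluded".

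**The concern.** An imbalance test asks whether a variable differs between arms, not whether it predicts sCD14. Under the rule, a strong predictor that happens to balance is never added, while an irrelevant variable that happens to differ must be. An irrelevant covariate that is associated with arm widens the confidence interval for the treatment effect and gives nothing back.

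Because the pool is not listed, the primary model also depends on how many variables are screened. Two analysts who both follow Section 9.5 can fit different models to the same data and report different main p-values.

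The rectal stratum is a separate gap. Stratified blocks balance it by design, so the imbalance rule would rarely bring it in. If it is prognostic, leaving it out makes the reported standard error too large.

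**Working it through.** **The plan's own figures.** A two-sample t-test (two-sided 5%, no covariates) gives 79.99% power at 0.909 SD with 20 per arm and 79.98% at 0.961 SD with 18 per arm. Multiplying by the SD of 0.54 gives 0.491 and 0.519 × 10^6 pg/mL. Section 9.4 reproduces, so the stated power rests on an unadjusted test.

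**Size of the pool.** Section 6.3.6 lists at least 4 haematology, 11 chemistry and 4 lipid values, and the schedule of events has all three panels at entry: 4 + 11 + 4 = 19. Section 9.5 does not say whether these count as clinical characteristics, so pools of 5, 15 and 19 are assumptions.

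**Chance that the rule triggers.** For k independent candidates this is 1 − 0.95^k: 22.6% (k=5), 53.7% (k=15), 62.3% (k=19). With 19 candidates correlated at 0.4, simulation gives 47.8%.

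**Variance inflation when it triggers.** With n=36, a covariate enters if |t| > 2.032 on 34 df. Then R² = t²/(t² + 34) = 0.108 and 1/(1 − R²) = 1 + t²/34 = 1.121. With n=40 the factor is 1.108. A typical triggered covariate lies beyond the threshold. Under the null, half of the triggered tests have p<0.025, where |t| = 2.345 and the factor is 1 + 5.50/34 = 1.16. With baseline and CD4 also in the model, the simulated median is about 1.17. The 12% is not a floor in that model: 12% to 15% of singly triggered covariates fell below it, with a minimum near 1%.

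**Power under the rule.** Assumptions not in the documents: 18 per arm, baseline correlation 0.6, continuous candidates, independent unless stated. The residual SD is then √(1 − 0.36) = 0.8, and 0.961 × 0.8 ≈ 0.77 SD is the effect that brings the adjusted model close to the planned 80%.

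| Candidates | Effect (SD) | Fixed model | With rule |
|---|---|---|---|
| 5, none prognostic | 0.77 | 77.7% | 75.9% |
| 15, none prognostic | 0.77 | 77.2% | 71.9% |
| 19, none prognostic | 0.77 | 77.7% | 71.1% |
| 19, correlated at 0.4 | 0.77 | 77.6% | 73.0% |
| 5, two prognostic (coefficient 0.4) | 0.77 | 77.3% | 77.7% |
| 5, all prognostic (coefficient 0.3) | 0.77 | 77.2% | 78.5% |
| 15, none prognostic | 0.961 | 92.2% | 88.2% |

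Repeat runs agreed; the loss with 19 independent candidates ranged from 6.0 to 6.6 points. Type I error under the rule with non-prognostic candidates was 4.9% to 5.0%. Screening 5 rather than 15 variables changed the significance verdict in 5.5% of trials at 0.77 SD, 3.4% at 0.961 SD and 1.5% under the null.

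**Rectal stratum.** Same assumptions, 0.77 SD, two subjects per arm dropped at random. Power is shown as omitted / included.

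| Stratum difference | Beyond baseline: power | Type I, omitted | Already at baseline: power | Type I, omitted |
|---|---|---|---|---|
| 0 | 77.4 / 77.1% | 5.2% | – | – |
| 0.3 SD | 76.4 / 77.4% | 4.4% | 77.3 / 77.2% | 5.0% |
| 0.5 SD | 74.0 / 77.2% | 4.3% | 77.5 / 77.8% | 4.8% |
| 0.8 SD | 69.3 / 77.3% | 3.2% | 77.8 / 79.0% | 4.6% |

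**Selective exclusion.** The primary set is as-treated, so a deliberately strong case was simulated: the DP arm loses its highest subjects on one prognostic candidate and placebo loses the same number at random. With 2 lost per arm and coefficients of 0.3 or 0.5, type I error was 5.9% or 6.9% for the fixed model and 5.0% or 4.9% under the rule. With 4 lost per arm it was 6.8% or 9.6% against 5.4% or 5.3%. A second set of runs gave 5.5% to 9.3% for the fixed model and 4.5% to 5.7% under the rule.

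**The case against.** The strongest reply is that the rule does useful work here. Section 9.5 restricts the primary analysis to subjects who stayed on treatment and allows replacements, so randomisation does not guarantee balance in the analysed set. The selective-exclusion runs show that the rule can hold type I error near 5% where a fixed model does not. This stands: deleting the rule without a replacement would have a real downside.

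Other points stand in part. The size of the loss rests on an assumed pool. A binary candidate tested by Fisher's exact test at 18 per arm triggers only 0.9% to 2.9% of the time (prevalence 10% to 50%), and several laboratory values overlap. Subset membership depends largely on agreeing to biopsies (Section 4.0), and nothing in the documents shows that it predicts plasma sCD14. This is also a pilot. Even so, Section 9.5 sets a two-sided 0.05 test on sCD14, and the model behind that test can be fixed in advance.

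A reader might infer three stronger charges, and the documents support none of them:
- That covariates could be chosen to suit the result. Selection uses baseline data and arm only, and the primary markers are assayed in batch after follow-up.
- That the rule inflates false positives. Under randomisation it does not.
- That the trial misses its planned power. At 0.961 SD with 15 irrelevant candidates, power is still 88% under the assumed baseline correlation.

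**Conclusion.** The point holds as one of model specification and efficiency. The pool is open, the selection criterion is the wrong one for precision, and a stratification factor is missing from the model.

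If candidates are not prognostic, a triggered covariate typically inflates the treatment-effect variance by about 17%, and overall power falls by about 2 to 6 points for 5 to 19 independent continuous candidates at 0.77 SD. The loss is smaller for correlated or binary candidates. It disappears or reverses if several are prognostic.

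Omitting the rectal stratum costs nothing if it is not prognostic, and at most about 1 point if its effect already shows in the baseline value. If it predicts week 12 sCD14 by 0.3 to 0.8 SD beyond baseline, the test is conservative and loses about 1 to 8 points. The documents do not say which case applies. Pool size, effect, baseline correlation and stratum effect are all assumptions.

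**What to change.** 1. Fix the primary ANCOVA as arm, baseline value of the same marker, CD4 count and rectal-subset stratum as randomised. State whether CD4 enters as a continuous value or as the stratum; the synopsis and Section 9.3 put a count of exactly 500 in different strata. The words 'as randomised' matter because, under Section 4.2.14, after an abnormal enrolment sigmoidoscopy "the participant will not be enrolled into the rectal tissue subset but will continue participation in the main study", and Section 6.2.2 allows biopsies up to 3 days after randomisation.
2. Replace the imbalance rule with a short list, named before unblinding, of covariates expected to predict the marker or exclusion from the as-treated set. Include all of them whatever balance is observed.
3. Report imbalance-adjusted models on the as-treated set as a labelled sensitivity analysis.

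Step 2 should not be skipped. Dropping the rule without naming such covariates can leave type I error above 5% if exclusions are strongly selective (5.5% to 9.6% over the assumed cases above).

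Cost: no new data, one degree of freedom for the stratum (about 0.3 power point if it is not prognostic) and one for each further single-parameter covariate. Section 9.5 is protocol text, so the change needs IRB review under Section 12.1.
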